## 7.5. AGEN2034 Overdose

An overdose is defined as any dose 5% greater than the highest daily dose included in the clinical trial protocol. Any overdose must be recorded in the trial medication section of the eCRF.

For monitoring purposes, any case of overdose, whether or not associated with an AE (serious or non-serious), must be reported to the Sponsor's or designated CRO's global drug safety department in an expedited manner using the SAE report form.

There is no data on AGEN2034 overdose to date. Data available with agents from the same class indicate that the correlation between dose and toxicity is relatively flat.

The investigator should use his or her clinical judgement when treating an overdose of AGEN2034.

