Furthermore, AGEN2034 and a marketed PD-1 inhibitor, nivolumab, have comparable efficacy profiles in a number of in vitro assays. Nivolumab, as well as another marketed PD-1 inhibitor, pembrolizumab, have shown clinical activity of this class and an overall acceptable safety profile, leading to regulatory approval for these drugs as a treatment of several malignancies.

In conclusion, the proposed safe starting dose of AGEN2034 is 1 mg/kg administered every 2 weeks to subjects with advanced malignancies who have progressed after standard treatment and for which no established therapy is available.

### 1.2.2. Dose in Phase 2

The choice of the Phase 2 dose was based on clinical data from the Phase 1 portion of this trial, evaluating AGEN2034 as monotherapy. Supportive clinical responses are also available from publications of similar-mechanism competitor nivolumab (anti PD-1; Opdivo®) as monotherapy since AGEN2034 has been shown to be functionally comparable to nivolumab.

Dosing for Phase 1 was guided by preclinical pharmacokinetics (PK), preclinical pharmacology, and comparisons to published results of nivolumab as monotherapy.

In Phase 1, a partial response was reported (Drescher et al 2018) in the 3 mg/kg every 2 weeks (q2wk) cohort that later was designated a complete response. Preliminary PK analysis of Phase 1 data suggests an AGEN2034 terminal half-life of approximately 10 days. Therefore, dosing AGEN2034 q2wk results in only a 25% increase in accumulation ratio compared to every 3 weeks. AGEN2034 dosed at 3 and 10 mg/kg q2wk resulted in average plasma AGEN2034 concentrations (Cavg) of 20 and 67 µg/mL, respectively (corresponding to 1.30 and 1.80 µg/mL when log-transformed). When these log-transformed values are compared with receptor occupancy and IL-2 AGEN2034 concentration-response profiles, the AGEN2034 Cavg values are clearly on the flat saturated part of the dose-response curves for these key pharmacodynamic parameters. Therefore, no additional benefit is expected for AGEN2034 doses greater than 3 mg/kg q2wk.

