#### **3.1. Phase 1 (Part A): Dose Escalation**

Phase 1 (Part A) of the study will consist of a standard 3+3 dose escalation with the following escalating dose levels and schedules:

- Part A1: 1, 3, and 10 mg/kg administered every 2 weeks
- Part A2: 6 and 10 mg/kg administered every 3 weeks

In Part A1, the first subject of each cohort will be observed for 16 days (i.e.,  $\geq 48$  hours after second dose) for occurrence of dose-limiting toxicity (DLT) before the second subject is administered trial medication. Thereafter, within each cohort in the dose escalation phase of Part A1, consecutively enrolled subjects may initiate treatment  $\geq 48$  hours after the prior enrolled

subject initiated treatment. Dose escalation will continue until the MTD is reached or the maximum planned dose level (10.0 mg/kg) is shown to be safe. The MTD is defined as the dose below which  $\geq 2$  DLTs are observed.

Once Part A1 is completed, enrollment for Part A2 will begin:

- If  $< 2$  DLTs are observed in dose escalation at the 10 mg/kg every 2 weeks dose level in Part A1, open enrollment will begin for Part A2 at the 6 mg/kg every 3 weeks dose level; enrollment of these subjects does not have to be sequential (that is, a wait of 48 hours between 2 subjects is not required). Once 10 subjects at the 6 mg/kg dose level have completed, open enrollment will begin for Part A2 at the 10 mg/kg every 3 weeks dose level; enrollment of these subjects does not have to be sequential (that is, a wait of 48 hours between 2 subjects is not required).
- If  $\geq 2$  DLTs are observed in dose escalation at the 10 mg/kg every 2 weeks dose level in Part A1, standard 3 + 3 dose escalation will continue with Part A2. Within each dose level cohort, consecutively enrolled subjects may initiate treatment  $\geq 48$  hours after the prior enrolled subject initiated treatment. Dose escalation will continue until the MTD is reached or the maximum planned dose level for Part A2 (10.0 mg/kg every 3 weeks) is shown to be safe.

[figure not shown]
Each subject will stay on the dose level and schedule assigned at trial entry. Subjects will receive AGEN2034 for a maximum of 24 months or until disease progression, unacceptable toxicity, or any criterion for stopping the study drug or withdrawal from the trial occurs.

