**Table 2: Phase 1 Dosing Regimens**

Part and Agent	Dose	Schedule	Duration of Treatment
Part A1: Dose Level 1			
AGEN2034	1 mg/kg IV 	Every 2 weeks	Up to 24 months
Part A1: Dose Level 2			
AGEN2034	3 mg/kg IV 	Every 2 weeks	Up to 24 months
Part A1: Dose Level 3			
AGEN2034	10 mg/kg IV 	Every 2 weeks	Up to 24 months
Part A2: Dose Level 1			
AGEN2034	6 mg/kg IV 	Every 3 weeks	Up to 24 months
Part A2: Dose Level 2			
AGEN2034	10 mg/kg IV 	Every 3 weeks	Up to 24 months

 Infusion time is 60 minutes (-10/+20 min)

In Phase 2, all subjects will receive AGEN2034 at a dose of 3 mg/kg IV over 60 minutes (-10/+20 min) every 2 weeks for up to 24 months.

In both Phases, subjects will be treated for up to 24 months, regardless of dose delays, as long as the subject meets criteria to remain on therapy.

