## 5.4.4. Dose Modifications and Treatment Delay

### 5.4.4.1. Dose Reductions

**No AGNE2034 dose reduction or escalation is allowed.** Each subject will stay on the dose levels assigned in the trial unless treatment needs to be stopped.

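### Read literally, Protocol 7.5 sets the overdose threshold at 10.5 mg/kg for every subject, 3.5 times the Phase 2 dose, so a doubled or tripled Phase 2 dose with no SAE or AESI needs no expedited report

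*Protocol*

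**What the plan says.** Protocol 7.5 gives the definition: "An overdose is defined as any dose 5% greater than the highest daily dose included in the clinical trial protocol". Two duties follow from it. The first is a data entry: "Any overdose must be recorded in the trial medication section of the eCRF". The second is an expedited report on the SAE form: "any case of overdose, whether or not associated with an AE (serious or non-serious), must be reported". The list of SAE criteria in Protocol 7.1.4 includes overdose and points back to 7.5 for its meaning, so the protocol has only this one definition.

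The dose levels are in Protocol 3.1 and Table 2. Part A1 of Phase 1 uses 1, 3 and 10 mg/kg every 2 weeks. The second part reads "Part A2: 6 and 10 mg/kg administered every 3 weeks". For Phase 2 the text below Table 2 says: "In Phase 2, all subjects will receive AGEN2034 at a dose of 3 mg/kg IV over 60 minutes", every 2 weeks. Protocol 5.4.4.1 fixes each subject at the assigned level: "No AGNE2034 dose reduction or escalation is allowed".

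SAP 7.6.1 takes up the same 5% margin with a different reference. It counts actual doses more than 5% above an adjusted planned dose, defined as the prescribed dose level times an adjusted weight. The adjustment allows for up to 10% weight loss, because the Pharmacy Manual does not require re-dosing for weight changes of that size.

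**The concern.** An overdose rule should detect a subject who receives materially more than was intended for that subject. The reference in 7.5 is instead the largest dose given to any cohort, with no mention of the subject's own dose level, cohort or phase. For a subject at 10 mg/kg the margin is 5%. For a Phase 2 subject at 3 mg/kg the same sentence leaves a margin of 250%.

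What is at stake is the expedited report and the SAE classification of an excess dose that causes no immediate event. Section 7.5 asks for that report even when there is no adverse event, and it says that no overdose data yet exist for this antibody. Under the literal rule, reports of Phase 2 infusions between about 3.15 and 10.5 mg/kg with no SAE or AESI would not be required. The compliance check in Protocol 6.4.1.11 would not replace them by itself: it compares volume infused with volume prepared, so a wrongly prepared bag that was fully infused would pass.

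**Working it through.** The documents state no numeric threshold, so there is no figure to reproduce. The thresholds follow by arithmetic.

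**Inputs**
- Dose levels: 1, 3, 6 and 10 mg/kg in Phase 1; 3 mg/kg in Phase 2 (Protocol 3.1, Table 2 and the text below it).
- Margin: 5% (Protocol 7.5; SAP 7.6.1).
- SAP adjusted weight: with baseline weight W0 and latest weight W, W_adj = W if W >= W0, otherwise the smaller of W0 and 1.1 x W.
- Body weight of 70 kg: an illustrative assumption.

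Dosing is every 2 or 3 weeks, so I read the daily dose as the dose of a single infusion.

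**Literal threshold under 7.5**
- Threshold = 1.05 x max(1, 3, 6, 10) = 1.05 x 10 = 10.5 mg/kg.
- Relative to the Phase 2 dose: 10.5 / 3 = 3.5.

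| Assigned level (mg/kg) | Literal threshold / assigned dose | 1.05 x assigned dose (mg/kg) |
|---|---|---|
| 1 | 10.5 | 1.05 |
| 3 | 3.5 | 3.15 |
| 6 | 1.75 | 6.3 |
| 10 | 1.05 | 10.5 |

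Only at 10 mg/kg do the two rules agree.

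**SAP limit in Phase 2**
- Weight at or above baseline: 1.05 x 3 = 3.15 mg/kg.
- Largest value after weight loss: 1.05 x 3 x 1.1 = 3.465 mg/kg of current weight.

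**In milligrams, for a current weight of 70 kg**
- Planned dose: 3 x 70 = 210 mg.
- SAP counts above 3.15 x 70 = 220.5 mg, or at most 3.465 x 70 = 242.6 mg after weight loss.
- Protocol 7.5, read literally, flags above 10.5 x 70 = 735 mg.
- Doubled dose: 2 x 210 = 420 mg. Tripled dose: 3 x 210 = 630 mg. Both exceed the SAP limit and both stay below 735 mg.

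So a doubled or tripled Phase 2 infusion is counted in the SAP exposure table but is not an overdose under 7.5, nor through the cross-reference in 7.1.4.

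**The case against.** The best defence is that the literal reading is not what the sponsor means. SAP 7.6.1 restates the rule with the dose prescribed in place of the dose included, and then computes it from the subject's dose level. Speaking of a daily dose for a drug given every 2 or 3 weeks also suggests loose drafting. I accept that this is probably a drafting slip. It does not remove the problem. The opening of Protocol Section 8 lets the SAP modify planned analyses; it does not change a reporting duty placed on sites in Section 7.

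A second defence is that the threshold is deliberate and marks exposure above anything planned in the trial. Some support exists. Section 7.5 says: "Data available with agents from the same class indicate that the correlation between dose and toxicity is relatively flat". Section 1.2.2 places concentrations at 3 and 10 mg/kg every 2 weeks "clearly on the flat saturated part of the dose-response curves". But the sentence is one rule for all cohorts. In the first-in-human 1 mg/kg cohort a tenfold error would have given 10 mg/kg, still below 10.5, at a level not yet tested. A rule meant to mark the edge of known exposure would not work that way, and the protocol nowhere says this was the intention. The flat relation limits the expected harm; it does not explain the definition.

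A third objection concerns consequence, and it stands. A reader might infer that excess doses would go unrecorded. The documents do not support that. SAP 7.6.1 sums actual doses, compares them with the planned dose on the eCRF and lists exposure details. SAP 6.2 lists all protocol deviations, and Protocol 10.1 asks investigators to tell the IRB about deviations. SAEs and AESIs remain reportable under 7.1.8 and 7.2.2 at any dose. What may be lost is the expedited report and SAE status of an event-free excess dose.

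Two further points stand. The change needs a protocol amendment, not only a memo. And any wording that refers to weight tolerance relies on a Pharmacy Manual that is not among the documents.

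**Conclusion.** The point holds as a minor fault in the wording of a safety-reporting rule. Read literally, 7.5 puts the overdose threshold at 10.5 mg/kg for every subject, 3.5 times the Phase 2 dose, against 3.15 mg/kg (at most 3.465 mg/kg of current weight) in the SAP's own count. Confidence is high for the literal threshold and the contrast with the SAP.

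Three stronger conclusions might be drawn, and the documents support none of them:
- That Phase 2 overdoses have gone unreported. No number of excess doses is given, and the Pharmacy Manual, eCRF conventions and SAE form instructions are not visible. Sites may already use the sensible reading.
- That subjects face a substantial added risk. Events remain reportable, and the protocol describes the dose-toxicity relation as relatively flat.
- That the efficacy results are affected. The response analysis does not use the overdose definition.

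The conclusion rests on reading the reference dose as the maximum over all cohorts and on treating the dose of one infusion as the daily dose.

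**What to change.** In the next protocol amendment, define overdose in 7.5 as *any administered dose more than 5% above the subject's planned dose for that infusion (assigned dose level x dosing weight, as permitted by the Pharmacy Manual)*, and notify sites. Section 7.1.4 then follows by cross-reference. For a Phase 2 subject of stable weight the threshold becomes 3.15 mg/kg. If the 10% tolerance is counted from the weight on which the current dose was set (an assumption to check against the Pharmacy Manual), the most it could reach is 3 x 1.05 / 0.9 = 3.5 mg/kg of current weight, one third of the literal 10.5.

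**Cost.** Protocol 10.1 sends changes in study conduct through an amendment, with IRB approval where necessary, and Phase 2 has about 60 centers. Because overdose is an SAE criterion, the rewording widens SAE ascertainment, and somewhat more dosing errors become expedited reports. For example, take a 210 mg dose set at 70 kg and left unchanged after a 12% loss to 61.6 kg. The planned dose is now 3 x 61.6 = 184.8 mg and the limit 1.05 x 184.8 = 194.0 mg, so the 210 mg infusion becomes reportable. Unchanged dosing within the 10% tolerance does not, under the same assumption. The eCRF already holds a planned dose, but the documents do not say how it is derived or whether the dosing weight is stored with it; check this before the wording is final. The rule can act only on infusions given after the change; for earlier ones the SAP 7.6.1 count remains the check.

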## 8. STATISTICAL CONSIDERATIONS

This section outlines the core elements of the planned statistical summaries and analyses for the data collected in this study.

Detailed methodology for summary and statistical analyses of the data collected in this study will be documented in a Statistical Analysis Plan (SAP), which will be maintained by the Sponsor. The SAP may modify the plans outlined in the protocol; however, any major modifications of the primary endpoint definition and/or its analysis will also be reflected in a protocol amendment. If, after the data are locked, changes are made to the SAP, then these deviations will be documented in the Clinical Study Report (CSR).

### 8.1. Sample Size

The study includes 2 phases: Phase 1: Dose Escalation Phase, and Phase 2: Expansion Phase. The total sample size for both phases is expected to be approximately 200 subjects.

#### 8.1.1. Phase 1

It is expected that approximately 50 subjects will be enrolled in the Phase 1 part of the study. The sample size in the Phase 1 is not driven by statistical hypothesis testing, but driven by clinical considerations. Final sample size in this phase may vary depending on the total number of dose levels to be tested, and subject replacement for DLT evaluation, if applicable.

#### 8.1.2. Phase 2

The aim in this phase is to detect preliminary evidence of clinical activity in subjects with metastatic cervical cancer. The primary endpoint is the ORR per IERC based on RECIST 1.1. ORR will be estimated as binomial proportion of best overall response (BOR) of confirmed PR

or CR and reported with 95% Wilson score confidence interval (CI); the CI will be interpreted as a plausible range for a true (unobserved) ORR.

Phase 2 is expected to enroll approximately 150 subjects. With 150 subjects in the final analysis, the power to exclude an ORR of 5% by the lower limit of the 95% Wilson score interval is 92.2% and 96.2%, assuming a true ORR of 12% and 13%, respectively. The sample size will provide  $\geq 77\%$  probability to observe an AE with an underlying rate of  $\geq 1\%$ . With 100 patients in the interim analysis, the power to exclude an ORR of 5% by the lower limit of the two-sided 95% Wilson score interval will be 77.4% and 85.2%, assuming a true ORR of 12% and 13%, respectively.

Historical published data may be used for the interpretation of the clinical significance of the study endpoints.

Interim analyses will be performed to assess the safety and efficacy (using the ORR and selected secondary efficacy endpoints) when (1) data are available for approximately 30 subjects treated for at least 3 months and (2) approximately 3 months after approximately 100 patients are dosed. No early stopping for efficacy will be performed, as a more complete safety assessment and evaluation of durability of responses is necessary for determination of risks and benefits. Consequently, interim analyses will not affect the overall type I error. A non-binding futility analysis may be performed using methods described in the statistical analysis plan. Additional interim analyses for safety and efficacy assessment may be performed.

## **8.2. Analysis Sets**

The following analysis sets will be defined and used separately for Phase 1 and Phase 2, as applicable:

- Phase 1 DLT analysis set: All subjects with data used for implementing the confirmation of the safety of the combination. These subjects should have received all study treatment administrations in the DLT evaluation period or should have stopped treatment because of DLTs in the DLT evaluation period.
- Safety analysis set: All subjects who have received  $\geq 1$  dose of trial treatment.
- Pharmacokinetics analysis set: All subjects who have completed  $\geq 1$  infusion of study drug, and who have provided sufficient concentration measurements.
- Evaluable efficacy analysis set: All subjects in Phase 2 who have received  $\geq 1$  dose of trial treatment and have measurable disease at baseline, according to the IERC assessment.

## **8.3. Description of Statistical Analyses**

### **8.3.1. General Considerations**

All data recorded during the study will be presented in individual data listings performed on the safety analysis set. All data will be evaluated as observed, and no imputation method for missing values will be used unless otherwise specified. All data will be presented in a descriptive manner. Statistical inference of the primary efficacy endpoint will be performed for the efficacy expansion cohort based on the pre-planned significance level.

Descriptive statistics will be used in general to summarize trial results, i.e., statistics for continuous variables may include means, standard deviations, medians, and ranges (min, max). Categorical variables will be summarized by counts and percentages. Unless otherwise specified, calculation of proportions will be based on the number of subjects in the analysis set of interest. Counts of missing observations will be included in the denominator and presented as a separate category if not otherwise specified in the SAP.

The DLT analysis set is the underlying dataset for determination of the safety. Safety analyses will be performed on the Safety analysis set. Analyses of PK variables will be performed on the PK analysis set. The primary analysis of the ORR and other efficacy variables will be based on the evaluable efficacy analysis set, defined as all subjects dosed with study drug who had measurable disease at baseline by IERC assessment. Details of the analysis will be described in the SAP.

Unless otherwise specified, endpoint analyses will be performed separately for Phase 1 and Phase 2.

### **8.3.2. Analysis of Primary Endpoints**

#### **8.3.2.1. In Phase 1: Dose-limiting Toxicity**

For determination of safety of AGEN2034, individual subject data from the Phase 1 portion of the trial will be reported. In addition, for final statistical analysis, the following will be summarized:

- At each dose level, number and proportion of subjects in the DLT analysis set who experience a DLT during the DLT evaluation period.
- At each dose level, number and proportion of TEAEs experienced by subjects in the DLT analysis set during the DLT evaluation period.

#### **8.3.2.2. In Phase 2: Objective Response Rate**

- The primary endpoint for Phase 2 is the confirmed ORR according to RECIST 1.1, as determined by an IERC. ORR will be estimated as the binomial proportion of patients with BOR of PR or CR, taking into account the following requirement for confirmation: for PR or CR, confirmation of the response according to RECIST 1.1 will be required at no sooner than 4 weeks after initial documentation of CR or PR. ORR will be reported with two-sided, 95% Wilson score CI.

### **8.3.3. Analysis of Secondary Endpoints**

The following secondary endpoints will be summarized.

#### **8.3.3.1. Efficacy Parameters**

Efficacy parameters, including confirmed ORR according to RECIST 1.1, as determined by investigator; disease control rate (DCR), defined as proportion of subjects with CR, PR, or SD for at least 12 weeks; duration of response (DOR) according to RECIST 1.1; time to response (TTR); and duration of stable disease, defined as time from treatment start until documented

progression, will be listed and summarized in Phase 2 using both IERC and investigator assessments.

DOOR and TTR will be summarized in only a subset of patients with confirmed response using the Kaplan-Meier method and displayed graphically, where appropriate. The median event time and 95% CI for the median will be provided. Duration of stable disease will also be summarized by the Kaplan-Meier method.

In addition, PFS, and OS time will be presented in subject listings, analyzed using Kaplan-Meier method and displayed graphically where appropriate. The median event time and 95% CI for the median will be provided.

### **8.3.3.2. Pharmacokinetic Parameters**

Both noncompartmental (NCA) and compartmental modeling (e.g., population PK [PopPK]) techniques will be used to analyze AGEN2034 PK.

The PK parameters to be estimated and reported may include, but may not be limited to: maximum drug concentration observed postdose at steady-state ( $C_{\max-ss}$ ); minimum observed concentration at steady-state ( $C_{\min-ss}$ ); area under the drug concentration-time curve (AUC) within a dosing interval within the time span  $t_1$  to  $t_2$  at steady-state ( $AUC_{(t_1-t_2)-ss}$ ); AUC from time of dosing (0 h) to time  $t$ , the time of last observation (calculated by linear trapezoidal summation) ( $AUC_{0-t}$ ); AUC from time of dosing (0 h) extrapolated to infinity (calculated by linear trapezoidal summation and extrapolated to infinity using  $C_{\text{last}}/\lambda_z$ ) ( $AUC_{0-\infty}$ ); time to maximum observed concentration (ie, time at which  $C_{\max}$  occurs) ( $t_{\max}$ ); terminal disposition rate constant, determined from the slope of the regression line of log (concentration) vs. time ( $\lambda_z$ ); terminal elimination half-life, determined as  $0.693/\lambda_z$  ( $t_{1/2}$  or HL); systemic clearance (CL); and volume of distribution (Vd).

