**Figure 1: In vitro Comparability of AGEN2034 and Nivolumab**

Head-to-head evaluation of AGEN2034 (black), commercial nivolumab (gray), or IgG4 isotype antibody (white) for: (A) - antibody binding to PD-1+ CD4+ T cells in cultures of *Staphylococcus* enterotoxin A (SEA)-stimulated human peripheral blood mononuclear cells (PBMCs); (B) - antibody-mediated blockade for PD-1 binding to PD-L1; (C) - inhibition of PD-1:PD-L1 signaling in a T-cell reporter assay; and (D) - T cell-induced IL-2 release in SEA-stimulated PBMC cultures. On the x-axis, log converted antibody concentration (log µg/mL) are shown. Data shown are representative of 2 independent experiments.

In this study, AGEN2034 demonstrated biphasic distribution after IV bolus dose administration and serum AGEN2034 concentrations increased in a manner commensurate with the increase in dose. There were no apparent differences in the exposure or disposition of AGEN2034 between male and female monkeys. The estimated mean half-life was 12.4 days in the recovery phase, and it is anticipated that steady-state conditions might be achieved in about 5 to 9 weeks. Anti-drug antibodies as a measure of immunogenicity of AGEN2034 in monkeys were assessed and revealed positive results at an incidence of 30 percent. Full toxicokinetic details are included in the AGEN2034 Investigator's Brochure.

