**Table 14: Phase 2 — Blood Sampling for Pharmacokinetic, Pharmacodynamic, Genetic, and Other Assessments**

Visit or Cycle	Day	For PK (see NOTE)	Additional Time Points for Rich PK Subset	For ADA	For PBMC	For [REDACTED]	For PGx
Screening	—	—	—	—	—	—	X 
Cycle 1	1	Predose  30 min ( $\pm$ 15 min) 	—	Predose 	Predose 	Predose 	—
	2	—	24 h ( $\pm$ 60 min) 	—	—	—	—
	8	—	168 h ( $\pm$ 4 h) 	—	—	—	—
Cycle 2	1	Predose 	—	Predose 	Predose 	Predose 	—
Cycle 3	1	Predose 	—	Predose 	Predose 	—	—
Cycle 4	1	Predose  30 min ( $\pm$ 15 min) 	—	Predose 	Predose 	Predose 	—
	2	—	24 h ( $\pm$ 60 min) 	—	—	—	—
	8	—	168 h ( $\pm$ 4 h) 	—	—	—	—
Cycles 5, 6, 12, 18, 24	1	—	—	Predose 	—	—	—
Discontinuation	—	X	—	X	X	X	—
Safety Follow-up Visit	4 wk after last dose	X	—	X	—	—	—
Follow-up Visit	3 mo after last dose	X	—	X	—	—	—

Abbreviations: ADA: antidrug antibody; [REDACTED] DNA: deoxyribonucleic acid; h: hour(s); mo: month; min: minute(s); PBMC: peripheral blood mononuclear cell; PGx: pharmacogenomics(s); PK: pharmacokinetic(s); wk: week(s).

 Blood sample for PGx is collected only if an ‘optional’ PGx consent is signed.

 Predose samples will be collected within 30 minutes before starting the AGEN2034 infusion.

 Blood samples collected on Day 1 at 30 ( $\pm$  15) minutes after the **end** of infusion

 As of Amendment 5 (27 September 2019), additional rich PK sampling will be collected in a subset of approximately 20 subjects in selected sites. Rich PK sampling will occur on Days 2 and 8 of Cycles 1 and 4 at 24 hours ( $\pm$  60 min) and 168 ( $\pm$  4) hours, respectively, after the **start** of the infusion.

**NOTE:** It is important to record all infusion start dates/times, infusion end dates/times, infusion interruption(s) start and end dates/times, infusion flush end dates/times, and blood sample dates/times completely and accurately (to the nearest minute). Blood for the 30-minute postdose PK samples should **never** be taken during the infusion and should be drawn at least 15 min after the end of infusion.

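### The linear trapezoidal rule across 6- to 7-day gaps on a falling curve overstates AUC0–t by about 1% to 9%; linear-up/log-down with prespecified λz points is better

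*Protocol*

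**What the plan says.** Protocol Section 8.3.3.2 announces two approaches: "Both noncompartmental (NCA) and compartmental modeling (e.g., population PK [PopPK]) techniques will be used to analyze AGEN2034 PK". For the noncompartmental part it names one integration rule, linear trapezoidal summation, for both AUC0–t and AUC0–∞ ("calculated by linear trapezoidal summation and extrapolated to infinity using" the last concentration divided by λz). It names no rule for the steady-state interval AUC and does not say which samples enter the λz regression.

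The sampling times come from the schedules:

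- **Phase 1 Part A1 (Table 11):** predose, 30 min, 2 h, 4 h and 24 h after the infusion, Day 8, then the next cycle's Day 1. The late gaps are about 6 and 7 days.
- **Phase 1 Part A2 (Table 12):** the same plus Day 15, giving gaps of 6, 7 and 7 days.
- **Phase 2 rich subset, about 20 subjects (Table 14, footnote 4):** "Rich PK sampling will occur on Days 2 and 8 of Cycles 1 and 4 at 24 hours" and 168 hours respectively. With the Cycle 2 predose sample, Cycle 1 has gaps of 6 and 7 days. Table 14 lists no Cycle 5 predose PK sample, so Cycle 4 sampling stops at 168 h.
- **Other Phase 2 subjects:** 30 min after the infusion, then the next predose, a single 14-day gap in Cycle 1.

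On curve shape, Protocol Section 1.2.2 says: "Preliminary PK analysis of Phase 1 data suggests an AGEN2034 terminal half-life of approximately 10 days". Section 1.1.2.1 says that in monkeys "AGEN2034 demonstrated biphasic distribution after IV bolus dose administration". The SAP (Sections 3.5 and 7.9) sends PK analysis to a separate plan that is not among the documents.

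**The concern.** A chord between two points on a convex falling curve lies above the curve, so the linear rule adds area on every declining segment. The error is systematic and does not average out over subjects. It grows with the gap and with any distribution phase, so it differs between sampling schedules.

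AUC and clearance are listed secondary PK parameters in both phases. ADA (both phases) and receptor occupancy (Phase 1) are to be correlated with exposure metrics. A rule that uses the same samples and is exact for a single exponential is available.

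**Working it through.** **Inputs.** Terminal half-life 10 days (Protocol 1.2.2), so k = ln 2/10 = 0.0693 per day; infusion 1 h; sampling times as above. The documents give no human distribution-phase values. I assumed a fast phase of 30–50% of the initial concentration with a half-life of 0.5–2 days.

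**Check of the half-life against the plan's own figure.** The protocol states that "dosing AGEN2034 q2wk results in only a 25% increase in accumulation ratio compared to every 3 weeks". With R = 1/(1 − e^(−kτ)), R(14) = 1.610 and R(21) = 1.304. The ratio is 1.234, or +23.4%; at 11 days it is +25.2%. The stated 25% is consistent with a half-life of about 10 days.

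**One gap, one phase.** Linear area over true area for a gap D is (kD/2)·coth(kD/2). At 10 days this gives +1.4% for 6 days, +2.0% for 7 days and +7.7% for 14 days. The log rule gives 0%.

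**One gap, two phases, by hand.** Take C(t) = 0.5·2^(−t) + 0.5·2^(−t/10), so C(1) = 0.7165, C(7) = 0.3117 and C(14) = 0.1895. From day 1 to day 7:

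- True: 0.355 + 2.290 = 2.645
- Linear: 6 × (0.7165 + 0.3117)/2 = 3.085, or +16.6%
- Log: 6 × (0.7165 − 0.3117)/ln(0.7165/0.3117) = 2.918, or +10.3%

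A sum of falling exponentials is also convex on the log scale. On each declining segment the order is therefore always true ≤ log ≤ linear. The log rule is closer but does not remove the error.

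**Whole schedules, 1-h infusion simulated.**

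| Schedule and curve | AUC0–t, linear | AUC0–t, linear-up/log-down |
|---|---|---|
| Part A1 or Phase 2 rich Cycle 1, one phase | +1.4% | −0.1% |
| Same, two phases (assumed) | +4.0% to +9.4% | +1.5% to +5.3% |
| Part A2, one phase | +1.5% | −0.1% |
| Phase 2 sparse Cycle 1, one phase | +7.5% | −0.1% |

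With one phase in Part A1, a half-life of 7 days (assumed) gives +2.75%, and 12.4 days (the monkey value) gives +0.86%.

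**Clearance.** The extrapolated share of AUC0–∞ is e^(−k·14) = 38% for q2wk and e^(−k·21) = 23% for q3wk. With one phase, Part A1 CL is −0.8% under the linear rule and +0.1% under log-down. With two phases the λz points decide the result. For the curve above:

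- Regression on days 1, 7 and 14: λz = 0.1015, tail 0.1895/0.1015 = 1.87
- Days 7 and 14 only: λz = ln(0.3117/0.1895)/7 = 0.0711, tail 2.67
- True tail: 0.1895/0.0693 = 2.73

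The three-point tail is short by 0.87 on a true total of 0.5/0.693 + 0.5/0.0693 = 7.93. The linear rule adds about 9.4% of 5.20, or 0.49, before day 14. The net AUC0–∞ error is about (0.49 − 0.87)/7.93 = −4.8%, so CL is overstated by about 5%.

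Over all the assumed two-phase curves on q2wk:

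| λz points | CL, linear | CL, log-down |
|---|---|---|
| Last three, including 24 h | +1.3% to +7.3% | +2.6% to +10.7% |
| Day 8 and next predose only | about −5% to +1% | about −3% to +4% |

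In Part A2 the last three points are all at Day 8 or later. CL there is about −2% to −6% with the linear rule and about −3% to +0.5% with log-down.

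**The case against.** Several counter-arguments have weight.

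- **The documented size is small.** On the only human figure given, the bias in well-sampled subjects is 1–2%. The larger figures rest on assumed distribution parameters; the biphasic finding is from monkeys. This stands.
- **The operative Phase 2 method is unseen.** The separate PK plan may already use another rule, and Protocol Section 8 lets the SAP modify its methods. This stands for Phase 2. The SAP covers only Phase 2, so nothing supplied changes the rule for Phase 1.
- **Little depends on AUC.** The correlation endpoints speak of exposure metrics without naming AUC, and a near-constant proportional bias on one schedule hardly moves a correlation. The Phase 2 dose rested on average concentrations and a clinical response (Protocol 1.2.2, including the dose-selection summary that closes it), and the primary ORR analysis is untouched. This stands, except that the bias differs between schedules.

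A reader might infer three stronger things that the documents do not support. One is that clearance is understated in every subject; the sign depends on λz, as shown. Another is that changing the integration rule alone is free of cost; on q2wk two-phase curves with the 24 h point in the fit, it moves CL further from the truth. The third is that exposure is overstated by roughly 30–60% in the approximately 130 Phase 2 subjects (150 − 20) outside the rich subset. That needs an assumed distribution phase and a noncompartmental AUC from two samples 14 days apart. The plan does not say it will do this: it also plans population PK, and its PK analysis set requires sufficient concentration measurements.

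**Conclusion.** The stated rule is not the best available for these schedules, and the direction of its AUC0–t bias is certain for a declining multi-exponential curve. The size is about +1.4% at the documented half-life with one phase. It is about +4% to +9% under the assumed distribution phase, against about 0% and +1.5% to +5% with the log rule.

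No general claim about clearance follows. The missing λz point rule matters at least as much for CL as the choice of trapezoid. The point is minor: it concerns secondary PK summaries, and population PK estimates do not use the trapezoidal rule. The figures assume noise-free profiles sampled on schedule.

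**What to change.** In Protocol Section 8.3.3.2 or the PK analysis plan, replace the linear rule with text such as:

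> AUC, including the steady-state interval AUC, will be calculated by the linear-up/log-down trapezoidal rule: linear up to the end-of-infusion peak, logarithmic on declining segments. λz will be estimated from post-distribution samples only; samples at 24 h or earlier will not be used. The minimum number of λz points will be stated. Noncompartmental AUC and CL will be reported for Phase 1 and the Phase 2 rich-sampling subset; exposures for other Phase 2 subjects will come from the population PK model.

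The cost is a software setting and a few sentences, with no new samples. AUC becomes slightly lower, and CL may shift a few percent either way. Once 24 h is excluded, the scheduled q2wk Cycle 1 samples leave two terminal points (Day 8 and next predose), against three in Part A2. If the plan requires three, q2wk profiles with only those samples give no noncompartmental CL, and the population model must supply it.
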